### Type of Participant and Disease Characteristics

1. Has documentation of PCR-confirmed SARS-CoV-2 infection with sample collection  $\leq 10$  days prior to the day of randomization.

*Note: PCR is the preferred method; however, with evolving approaches to laboratory confirmation of SARS-CoV-2 infection, other molecular or antigen tests that detect viral RNA or protein are allowed if authorized for use in the country. Serological tests that detect host antibodies generated in response to recent or prior infection are not allowed.*

2. Had initial onset of signs/symptoms attributable to COVID-19 for  $\leq 10$  days prior to the day of randomization and  $\geq 1$  sign/symptom attributable to COVID-19 present at randomization.
3. Requires medical care in the hospital for ongoing clinical manifestations of COVID-19 (not just for public health or quarantine purposes).
4. Has mild, moderate, or severe COVID-19 (Appendix 9).
5. Is willing and able to take oral medication.

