**Exploratory:**

- Change from baseline in SARS-CoV-2 RNA titer in nasopharyngeal and oropharyngeal swabs separately at various timepoints
- Percentage of participants with undetectable SARS-CoV-2 RNA in nasopharyngeal and oropharyngeal swabs separately at various timepoints
- Viral RNA mutation rate as assessed by comparison of baseline and post-baseline virus sequencing (Part 1)
- Mean change from baseline in inflammatory biomarkers (eg, IL-6, hs-CRP, ESR, D-dimer, PCT)

In addition to the endpoints listed above, survival, supplemental oxygen use, and hospitalization status at the LFU visit (Month 7) will also be summarized.

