### **9.5 Analysis Populations**

#### **9.5.1 Efficacy Analysis Populations**

The MITT population will serve as the primary population for the analysis of efficacy data for both parts of this study. The MITT population consists of all randomized participants who received at least 1 dose of study intervention. Part 1 (Phase 2) and Part 2 (Phase 3) of the study will be analyzed separately for efficacy endpoints. Therefore, the MITT population for Part 2 will not include Part 1 participants, and vice versa.

A supportive analysis using the Per-Protocol population will be performed for primary and secondary efficacy endpoint(s) for Part 2. The Per-Protocol population excludes participants due to deviations from the protocol that may substantially affect the results of the primary efficacy endpoint.

The final determination on protocol deviations, and thereby the composition of the Per-Protocol population, will be made prior to the final unblinding of the database and will be documented in a separate memo.

Participants will be included in the treatment group to which they are randomized for the analysis of efficacy data using both the MITT and Per-Protocol populations.

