The viral RNA endpoints at earlier time points (Day 3 and EOT) will be important for the dose selection decision from Part 1 of the study. Change from baseline in SARS-CoV-2 RNA titer, calculated as  $\log_{10}$  (post) minus  $\log_{10}$  (baseline), as measured by quantitative RT-PCR of samples from NP and OP swabs will be summarized separately by treatment group and time point. The DAO approach will be used to handle missing data for these summary statistics. In addition to summary statistics, treatment differences in change in SARS-CoV-2 RNA titer from baseline over time will be estimated using longitudinal models. Graphical presentations of the change from baseline will be presented and the impact of baseline viral RNA level will be explored using subgroup analyses (defined by level of baseline viral RNA) and analyses/summaries that exclude participants with low baseline levels (eg, viral RNA  $<10^6$  copies/mL).

Percentage of participants with undetectable viral RNA (below limit of detection) as measured by qualitative RT-PCR of samples from NP and OP swabs will be summarized separately by treatment group and time point. Between-treatment differences and 95% confidence intervals will be estimated using the stratified Miettinen and Nurminen method [Miettinen, O. 1985].

A detailed analysis strategy for key efficacy endpoints is listed in [Table 5](#). The strategy to address multiplicity issues with regard to multiple efficacy endpoints and interim analyses is described in Section 9.7, Interim Analyses and in Section 9.8, Multiplicity.

Table 5 Analysis Strategy for Key Efficacy Endpoints

Endpoint/Variable (Description, Time Point)	Primary vs. Supportive Approach a	Statistical Method b	Analysis Population	Missing Data and Data Imputation Approach
Primary Endpoint				

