### **IA2 - Part 1: Dose Selection**

This analysis is targeted to occur at the completion of Phase 2 after ~300 participants (~75 per group) have completed the Day 29 visit. This IA will be used to evaluate the dose/exposure-response to select the dose for Phase 3. The relationship between dose and PK (plasma NHC and PBMC NHC-triphosphate), virologic endpoints (eg, rate of virologic RNA clearance, viral RNA mutation rate), safety, and key efficacy results will be evaluated. PK and virology data from other ongoing studies of MK-4482 including MK-4482-002 will also be examined at the time of this IA to inform the Phase 3 dose selection.

Additional details regarding dose selection criteria will be described in the siDMC Charter. The dose selected for Phase 3 will be communicated directly to sites in accordance with local regulatory requirements.

Part 2 (Phase 3) enrollment will be initiated after all participants for Part 1 of this study have completed the Day 29 visit, and after the completion of the IA2 analysis.

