### 9.9.2 Sample Size and Power Calculations for Virology Analyses (Part 1)

The sample size for Part 1 was not determined based on a specific hypothesis for a specific endpoint. The selection of the dose to advance to Part 2 will be based on analyses of the totality of data available across the MK-4482 clinical program. Three hundred participants (75 per group) will be sufficient to provide reasonable precision to discriminate between treatment groups with regard to the virology endpoints. An important endpoint for assessing the dose-response relationship is viral RNA change from baseline in SARS-CoV-2 RNA titer, calculated as  $\log_{10}$  (post) minus  $\log_{10}$  (baseline). Approximately 80% of this cohort (60/group) is expected to have baseline viral load of at least  $10^6$  copies/mL. A 1 log-unit difference between treatment groups in the population mean is considered to be clinically relevant. [Table 8](#) provides power calculations for true log differences of 0.75 to 1.25 and for various assumptions about the true underlying standard deviation.

Table 8 Power by Detectable Difference and Standard Deviation Viral RNA Change from Baseline ( $\log_{10}$  copies/mL) N=60/group,  $\alpha=0.025$ , 1-sided

Standard Deviation	Between Group Difference ( $\log_{10}$ copies/mL)		
	-0.75	-1.00	-1.25
1.25	90%	99%	>99%
1.5	78%	95%	>99%
1.75	64%	87%	97%

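### The percentage with undetectable RNA does not require detectable RNA on the Day 1 swab of the same type, so participants already negative on Day 1 dilute the difference between arms

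*Combined protocol and SAP*

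**What the plan says.** Section 9.4.1.1 lists as an exploratory endpoint: "Percentage of participants with undetectable SARS-CoV-2 RNA in nasopharyngeal and oropharyngeal swabs separately at various timepoints". Section 9.6.1 words it as "Percentage of participants with undetectable viral RNA (below limit of detection) as measured by qualitative RT-PCR of samples from NP and OP swabs", and adds: "Between-treatment differences and 95% confidence intervals will be estimated using the stratified Miettinen and Nurminen method". Neither place requires RNA to have been detectable at baseline. The primary efficacy population has no such requirement: "The MITT population consists of all randomized participants who received at least 1 dose of study intervention" (Section 9.5.1).

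Baseline RNA level is addressed in Section 9.6.1 only in the preceding paragraph, on change in titer. It plans subgroups by baseline RNA and summaries leaving out low baselines (for example, below 10^6 copies/mL). The paragraph on the percentage undetectable does not repeat this and gives no rule for missing swabs.

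Entry does not guarantee a positive Day 1 study swab. Inclusion criterion 1 reads "Has documentation of PCR-confirmed SARS-CoV-2 infection with sample collection" up to 10 days before the day of randomization, and "other molecular or antigen tests that detect viral RNA or protein are allowed if authorized for use in the country". Section 8.1.2 accepts several sample types, including mid-turbinate and saliva. Appendix 2 makes the qualifying test local, while the endpoint uses the study's own NP and OP swabs, analysed separately.

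Section 9.6.1 calls the Day 3 and EOT viral RNA endpoints important for choosing the Part 2 dose. Section 9.7 (IA2) lists "virologic endpoints (eg, rate of virologic RNA clearance, viral RNA mutation rate" among the relationships to be examined.

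**The concern.** An undetectable result at Day 3 or EOT can arise in two ways: RNA was present on Day 1 and has gone, or it was not detectable in that swab type to begin with. Only the first says anything about antiviral effect. The endpoint as written counts both.

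Participants already negative on Day 1 are spread over the arms by randomization. They raise every arm's percentage by a similar amount, shrink the difference between arms, and add variation through chance imbalance in their number. The effect is greatest at early visits if true clearance is still low there, because a few baseline negatives can then make up a large share of the apparent responders. At stake is how well this summary separates 200 mg, 400 mg, 800 mg and placebo in Part 1.

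**Working it through.** **The plan's own virology figure.** The only virology power in the plan is Table 8 (Section 9.9.2), for change in titer with 60 per group and one-sided alpha 0.025. For a difference of 1.00 and SD 1.5: 1.00 / (1.5 × √(2/60)) = 3.651, and Φ(3.651 − 1.960) = 95.5% (95.2% with the noncentral t); the table gives 95%. All nine cells reproduce in this way. The 60 per group is 75 × 0.80, from the statement "Approximately 80% of this cohort (60/group) is expected to have baseline viral load of at least" 10^6 copies/mL. No power is given for the percentage undetectable, so there is no stated figure to check for that endpoint.

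**Inputs for the percentage endpoint**
- n = 75 per arm (Sections 4.1 and 9.9.2).
- q, the fraction negative on Day 1 in a given swab type and still negative at the later visit: not in the documents. Assumed 5%, 10% and 20%. The plan expects about 20% below 10^6 copies/mL, so 20% would apply only if every one of them were below the limit of detection.
- True clearance among participants with detectable baseline RNA: not in the documents. Assumed pairs are 5% vs 15%, 15% vs 35% and 50% vs 70%.

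**Formulas**
- All-participant rate: P = q + (1−q)p. Hence P1 − P0 = (1−q)(p1 − p0).
- Restricted analysis: rates p0 and p1 on an expected 75(1−q) per arm, which is 71.25, 67.5 and 60.
- Power (two-sided 5%, unpooled normal approximation): Φ(difference/SE − 1.960), with SE = √{[r0(1−r0) + r1(1−r1)]/n} for the rates r0, r1 and size n analysed.

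**One case in full: q = 10%, 5% vs 15%**
- All participants: P0 = 0.10 + 0.90 × 0.05 = 0.145 and P1 = 0.10 + 0.90 × 0.15 = 0.235. Difference 0.090. SE = √[(0.1240 + 0.1798)/75] = 0.0636. Power = Φ(1.414 − 1.960) = 29%.
- Detectable baseline only: difference 0.100. SE = √[(0.0475 + 0.1275)/67.5] = 0.0509. Power = Φ(1.964 − 1.960) = 50%.

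**Full grid: power on all participants vs on those detectable at baseline**

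| q | 5% vs 15% | 15% vs 35% | 50% vs 70% |
|---|---|---|---|
| 5% | 39 vs 52% | 75 vs 81% | 69 vs 70% |
| 10% | 29 vs 50% | 67 vs 79% | 65 vs 68% |
| 20% | 19 vs 46% | 53 vs 74% | 57 vs 63% |

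The restricted analysis has the higher power in all nine cells despite fewer participants. The gap runs from 1 point (70 − 69) to 27 points (46 − 19).

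**Cross-check with other rates** (one-sided 0.025, q = 10%). For 5% vs 20%, power is 53% on all participants and 76% restricted. For 20% vs 40%, it is 63% and 72%. Direction and order of size agree.

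**Chance imbalance in Day 1 negatives.** The SD of the difference between two arms is √[2q(1−q)/75]: 3.6 points at q = 5%, 4.9 at 10% and 6.5 at 20%.

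**The case against.** The strongest case against has five parts.

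- **The size is unknown.** Below 10^6 copies/mL is not below the limit of detection, and the plan states no limit. Participants must have onset within 10 days and a symptom still present, and Section 4.2.3 describes viral load as persisting 7 to 12 days in moderate cases and up to 2 weeks in severe ones. The true q may be small. This stands: an old or antigen qualifying test makes q above zero plausible but does not size it.
- **No test is planned.** The plan reports differences and 95% intervals for an exploratory endpoint, and Part 1 was not sized on any one hypothesis. This stands, so the power figures only illustrate the loss of signal relative to its standard error.
- **The dose decision rests on much else.** It also uses PK, titer, safety, efficacy and data from the wider program. The modelling plans and the siDMC charter are separate documents. A reader might infer that a diluted percentage would drive the dose choice; the documents do not show this, nor that the clearance rate named at IA2 is this percentage.
- **The titer analysis already handles low baselines.** This stands for titer. Even a generous reading that extends it to the percentage would give added exploration, not a defined denominator.
- **The label is literal.** The endpoint is called percentage undetectable, and that is what it measures. This is fair, but the percentage cannot then be read as clearance without the Day 1 status.

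A reader might also infer a bias in favour of a dose. The documents do not support that: Day 1 status is fixed before dosing and spread by randomization.

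**Conclusion.** The gap is real and modest. On the plain reading of Sections 9.4.1.1, 9.5.1 and 9.6.1, a participant negative on Day 1 who stays negative counts as a responder. The all-participant denominator follows from the endpoint wording together with the MITT definition; it is not spelled out for this endpoint.

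The consequence is attenuation by (1−q) plus noise, not a false signal. With q between 5% and 20%, a true difference loses 5% to 20% of its size. The power loss is small when clearance is already common (1 to 6 points for 50% vs 70%) and larger when it is rare (13 to 27 points for 5% vs 15%, a pair with only about half power even under the restricted analysis). All of this rests on assumed q and clearance rates, and on baseline negatives remaining negative. It would be wrong to treat 20% as the plan's estimate of the baseline-negative share.

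**What to change.** In Sections 9.4.1.1 and 9.6.1, define the main analysis as the percentage undetectable among MITT participants with detectable RNA on the Day 1 pre-dose swab of the same type (NP or OP). Keep the stratified Miettinen and Nurminen method. As supportive output, show the all-participant percentage and, by arm and swab type, the number negative on Day 1 and the number with a missing or invalid Day 1 swab. State how missing post-baseline swabs are handled, since the data-as-observed rule is given only for the titer summaries.

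The cost is wording and one filter. The Day 1 swabs are already scheduled, and the filter uses a pre-dose value, so randomized comparability is kept. Because the endpoint is exploratory, Section 9 allows the change to be documented in the sSAP before unblinding. The downside is a somewhat smaller denominator, which also drops participants without a valid Day 1 swab of that type; this is why those counts should be reported by arm.

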## 9.6.2 Statistical Methods for Safety Analyses

Safety and tolerability will be assessed by clinical review of all relevant parameters including AEs, laboratory values and vital signs.

The analysis of safety results will follow a tiered approach as shown in [Table 6](#). The tiers differ with respect to the analyses that will be performed. For this protocol, only ECIs are considered Tier 1 events. Adverse events (specific terms as well as system organ class terms) and events that meet predefined limits of change (PDLCs) in laboratory values or vital signs will be classified as belonging to "Tier 2" or "Tier 3" based on the number of events observed.

### **Tier 1 Events**

Safety parameters or AEs of special interest that are identified a priori constitute "Tier 1" safety endpoints that will be subject to inferential testing for statistical significance with p-values and 95% CIs to be provided for between-treatment differences in the proportion of participants with events; these analyses will be performed using the unstratified Miettinen and Nurminen method [Miettinen, O. 1985], an unconditional, asymptotic method. Since the stratification factors are not considered to be related to safety endpoints, they will not be included as stratification factors in the safety analyses.

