#### **6.3.2 Stratification**

Intervention randomization will be stratified according to the following factors:

1. Time from symptom onset prior to the day of randomization ( $\leq 5$  days,  $>5$  days)
2. Age ( $\leq 60$  years,  $>60$  years)
3. Remdesivir use for treatment of the index diagnosis of COVID-19 prior to or at the time of randomization (yes, no)

Based on the viral kinetics of SARS-CoV-2 and the mechanism of action of MK-4482, treatment with antiviral therapy is likely to have a greater benefit with early treatment ( $\leq 5$  days) rather than late treatment ( $>5$  days). Older age is also associated with more severe outcomes, and the WHO notes that people older than 60 years are at higher risk for severe illness due to COVID-19. Finally, remdesivir has been demonstrated to shorten the time to recovery in hospitalized patients with COVID-19 and may be used concurrently in this study. The selection of these criteria as stratification factors will help ensure that the treatment groups will be well balanced within each stratum and the study results will not be confounded by factors suspected to have a potential impact on a participant's response to study intervention.

Of note, enrollment of participants with severe COVID-19 (Appendix 9) will be limited to 50% of the total planned sample size in both Parts 1 and 2.

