Statistical Methods for Key Safety Analyses	P-values (Tier 1 endpoints) and 95% CIs (Tier 1 and Tier 2 endpoints) will be provided for between-treatment differences in the percentage of participants with the adverse events; these analyses will be performed using the unstratified Miettinen and Nurminen method [Miettinen, O. 1985].
Interim Analyses	
There will be 3 interim analyses during the study.
 
IA1 - Part 1: Dose Evaluation
 
This IA will be used to review data to inform dose selection models and analyses.
 
IA2 – Part 1: Dose Selection
 
This IA will be used to evaluate the dose/exposure-response to select the dose for Phase 3.
 
IA3 – Part 2: Futility/Early Efficacy
 
The purpose of this IA is to allow for early stopping in the case of futility and to allow for the initiation of marketing authorization applications in the case of a positive efficacy finding.
 
Additional details about interim analyses are in Section 9.7.

Multiplicity	Multiplicity adjustments for interim analyses regarding type I error control are described in Section 9.7. Multiplicity adjustment strategy for sequential hypothesis testing is specified in Section 9.8.
Sample Size and Power	
The total sample size for primary efficacy assessment (Part 2) will be ~1000 participants (~500 for the selected dose of MK-4482 and ~500 for the placebo group). The study has overall power of 90% to demonstrate that participants treated with MK-4482 have a higher rate of sustained recovery than participants treated with placebo at an overall one-sided, 2.5% alpha-level, if the underlying constant sustained recovery rate ratio between treatment groups is 1.3.
 
Additional details and assumptions for sample size and power calculation are in Section 9.9.

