#### **9.4.2 Safety Endpoints**

A description of safety measures is contained in Sections 8.3 and 8.4. The analysis of safety results is described in Section 9.6.2.

The safety analysis endpoints include:

- The proportion of: 1) participants with at least 1 AE; 2) participants with at least 1 drug-related AE; 3) participants with at least 1 SAE; 4) participants with at least 1 serious and drug-related AE; 5) participants who discontinued study intervention due to AE; 6) participants who discontinued study intervention due to a drug-related AE; and 7) participants with AE(s) leading to death. The AE reporting period is from the time of randomization through 14 days following cessation of treatment. Additional reporting periods will be used as appropriate (eg, throughout the study for SAE).
- Events of Clinical Interest specified in Section 8.4.7.

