### **9.5.2 Safety Analysis Populations**

Safety Analyses will be conducted in the APaT population, which consists of all randomized participants who received at least one dose of study treatment. Participants will be included in the treatment group corresponding to the study treatment they actually received for the analysis of safety data using the APaT population. This will be the treatment group to which they are randomized except for participants who take incorrect study treatment for the entire treatment period; such participants will be included in the treatment group corresponding to the study treatment actually received. Part 1 (Phase 2) and Part 2 (Phase 3) of the study will be combined for the final analysis of safety endpoints. The data presentations will focus on the selected dose group for MK-4482 and placebo.

At least one laboratory value or vital sign obtained subsequent to at least one dose of study treatment is required for inclusion in the analysis of the respective safety parameter. To assess change from baseline, a baseline measurement is also required.

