### 9.9.3 Sample Size and Power Calculations for Safety Analyses (Part 2)

Part 1 (Phase 2) and Part 2 (Phase 3) of the study will be combined for the final analysis of safety endpoints. The planned sample size for safety analysis will be 575 for MK-4482 selected dose group and placebo. The probability of observing at least 1 of a particular type of AE in this study depends on the number of participants treated and the underlying percentage of participants with an AE in the study population. If the underlying incidence of an AE is 1%, there is a 99.7% chance of observing at least one AE among 575 participants in the treatment group. If no AE of that type is observed among the 575 participants in any treatment group, this study will provide 97.5% confidence that the underlying percentage of participants with the AE is < 0.64% (1 out of every 156 participants).

[Table 9](#) summarizes the percentage point differences between the 2 treatment groups that could be detected with 90% probability for a variety of hypothetical underlying incidences of an AE. These calculations assume 575 participants in each group and are based on a 2-sided 5% alpha level. The calculations are based on Farrington and Manning [Farrington, C. P. and Manning, G. 1990]. No multiplicity adjustments were made.

Table 9 Differences in Incidence of AE Rates Between the 2 Treatment Groups That Can be Detected With an ~90% Probability (Assuming 2-sided 5% Alpha Level with 575 Participants in Each Group)

Incidence of Adverse Event		Risk Difference
Placebo (%)	MK-4482 (%)	Percentage Points
1.0	4.0	3.0
5.0	10.0	5.0
10.0	16.5	6.5
20.0	28.2	8.2
30.0	39.1	9.1
40.0	49.5	9.5

Incidences presented here are hypothetical and do not represent actual adverse experiences in either group. Calculations are based on Farrington and Manning [Farrington, C. P. and Manning, G. 1990].

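### Section 9.6.2 drops age from the safety analyses as unrelated to safety, which 6.3.2 contradicts; for common categories such as any SAE this forgoes a small gain in precision

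*Combined protocol and SAP*

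**What the plan says.** Randomisation is stratified by time from symptom onset, age (60 or under, over 60) and remdesivir use (6.3.2). Of age, 6.3.2 says: "Older age is also associated with more severe outcomes".

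For safety, the summary in 9.1 covers Tier 1 and Tier 2 together: "these analyses will be performed using the unstratified Miettinen and Nurminen method". The reason appears in 9.6.2 under Tier 1 Events, but it is worded for the safety analyses as a whole: "Since the stratification factors are not considered to be related to safety endpoints, they will not be included as stratification factors".

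The safety endpoints in 9.4.2 include participants with at least one SAE and "7) participants with AE(s) leading to death". Section 10.3.2 makes death, and admission or prolonged hospital stay, criteria for an SAE. Section 8.4.6, despite its heading, requires hospitalisations and deaths to be reported under 8.4.1 until 14 days after treatment ends. Parts 1 and 2 "will be combined for the final analysis of safety endpoints" (9.5.2).

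Section 9.6.1 already plans a stratified Miettinen and Nurminen analysis for undetectable viral RNA. It uses the unstratified version for Day 29 mortality for a different reason: few expected deaths and many strata.

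**The concern.** A factor chosen for randomisation because it predicts severe outcomes cannot also be assumed unrelated to an endpoint that counts severe outcomes. When randomisation is balanced on a prognostic factor and the analysis ignores it, the standard error of the risk difference includes between-stratum variation that the design has already removed. The interval stays valid but is somewhat wider than it needs to be. In a safety comparison, unneeded width is not a neutral form of caution, because it makes a real excess slightly harder to distinguish from none. What is at stake is a modest amount of precision for the more common safety categories, and a stated reason that the protocol itself contradicts.

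**Working it through.** **Inputs from the documents.** Section 9.9.3: "These calculations assume 575 participants in each group and are based on a 2-sided 5% alpha level". The Table 9 differences are those that "could be detected with 90% probability for a variety of hypothetical underlying incidences of an AE". The placebo and MK-4482 pairs run from 1% vs 4% to 40% vs 49.5%, and the table notes: "Incidences presented here are hypothetical and do not represent actual adverse experiences in either group". No SAE rate, age distribution or age-specific rate is given.

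**Assumptions.** Share aged over 60: 30% or 50%. Risk ratio, over 60 to 60 or under: 2, 3 or 5. Treatment effect constant across age either as a ratio or as a difference.

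**Step 1: reproduce Table 9 without strata.** Power = Φ[(d − 1.96·s0)/s1], where d is the risk difference, s0 = √(2p̄(1−p̄)/575), s1 = √((p1(1−p1)+p2(1−p2))/575) and p̄ is the mean of p1 and p2. For 10% vs 16.5%: s0 = 0.0200, s1 = 0.0199, and (0.065 − 0.0392)/0.0199 = 1.30, giving 90.3%. The six rows give 90.4, 89.7, 90.3, 90.3, 90.2 and 90.1%. The stated 90% is therefore already the unstratified figure.

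**Step 2: the expected gain.** With share w over 60, stratifying reduces each arm's variance from p(1−p) to p(1−p) − w(1−w)(p_old − p_young)². Averaging over arms with the same age-specific rates and w = 0.5:

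- 10% and 25%: p = 0.175, variance 0.1444, reduction 0.25 × 0.15² = 0.0056. Ratio 0.961; interval about 2.0% narrower.
- 10% and 40%: p = 0.25, variance 0.1875, reduction 0.25 × 0.30² = 0.0225. Ratio 0.880; about 6.2% narrower.
- 1% and 3%: p = 0.02, variance 0.0196, reduction 0.25 × 0.02² = 0.0001. Ratio 0.995; about 0.3% narrower.

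**Step 3: the planned method itself.** Miettinen and Nurminen intervals were simulated at 575 per arm, unstratified against stratified by age (Cochran–Mantel–Haenszel weights, 20,000 trials per scenario). Here power means the probability that the lower 95% limit exceeds 0.

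| Placebo vs MK-4482 | Change in mean width from stratifying | Change in power (points) |
|---|---|---|
| 1% vs 4% | −0.3% to +3.2% | 0 to +0.1 |
| 3% vs 3% | +0.2% to +1.1% | none of note |
| 5% vs 10% | −0.9% to +0.7% | +0.2 to +1.0 |
| 10% vs 16.5% | −0.4% to −3.3% | +0.2 to +1.9 |
| 20% vs 28.2% | −1.2% to −10.4% | +0.4 to +3.0 |

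Of the 24 scenarios at 10% and 20%, 22 lie between 0.4% and 5.9% narrower. The other two (7.7% and 10.4%) both need a fivefold age risk ratio with 30% aged over 60. At 20% incidence and a risk ratio of 2 the interval is 1.2% to 1.8% narrower. Using all eight randomisation strata gave practically the same result as age alone.

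**Step 4: calibration.** With equal 5% rates and an age risk ratio of 5, the unstratified interval excluded 0 in 4.8% of trials, so it does not exclude 0 too often.

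**The case against.** Unstratified Miettinen and Nurminen is valid, prespecified and slightly conservative, and the plan's own power statement assumes it. The quoted sentence sits under Tier 1, which 9.6.2 limits to the events of clinical interest in 8.4.7: liver tests, platelets, and amylase or lipase. Section 6.3.2 does not link age to any of these, and at low incidence stratifying tends to widen the interval slightly. SAEs are Tier 2, where 9.6.2 calls the intervals descriptive and provides no p-value. The gain depends on rates that the documents do not give. All of this stands. It removes any case for stratifying Tier 1 and keeps the point small. It does not rescue the stated reason, which covers all safety analyses and is wrong about age for SAEs. Nor does the sparse-data argument in 9.6.1 carry over to any SAE split into two age groups.

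A reader might infer more than the documents support:

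- *Intervals for fatal AEs are too wide.* AEs leading to death are an endpoint in 9.4.2 but appear neither in the broad Tier 2 list nor in Table 6, so no interval is planned for that category. At 1% to 5% incidence, where such events might lie (an assumption), stratifying changes width by −0.9% to +3.2%.
- *The trial loses stated sensitivity to harm.* Step 1 shows that it does not.
- *Pooling the two parts biases the comparison.* The selected dose and placebo are allocated 1:1 in each part (about 75 + 500 = 575 per group), so study part is not a confounder.

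**Conclusion.** The blanket reason in 9.6.2 conflicts with 6.3.2 for age wherever the endpoint captures severe outcomes, and it should not stand. The consequence is a small loss of precision for common broad categories: usually 0.4% to 6% of interval width, with 10.4% the largest value found, and 0.2 to 3.0 points of power at 10% to 20% placebo incidence. Those sizes depend on the assumed age shares, risk ratios and incidences; incidences above 20% were not simulated. For rare events and the Tier 1 laboratory events there is essentially nothing to gain. This is a worthwhile tidy-up, not a flaw that hides harm or invalidates the planned safety analysis.

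**What to change.** In 9.6.2:

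1. Delete the sentence saying that the stratification factors are unrelated to safety.
2. For the broad Tier 2 categories, at least any AE and any SAE, specify the stratified Miettinen and Nurminen method with age group (60 or under, over 60) as the stratum, and name the weights, since 9.6.1 gives none for its stratified analysis.
3. Keep the unstratified method for Tier 1 events and for sparse specific AEs, justified by sparse data as 9.6.1 does for mortality.
4. Align the one-line description of the safety method in 9.1.

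The cost is SAP wording and a small amount of programming. The method is already planned for the virology endpoint, age group is already recorded for randomisation, and neither sample size nor data collection changes.
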